2. STUDY SCHEDULE AND TIMELINE

IBSOS is a prospective, randomized, multi-site clinical trial comparing three types of psychotherapy delivered in an individual format for severely affected adults with IBS. After a four-week baseline data collection period, participants will be randomly assigned to receive either four-session self-administered CBT, 10-session therapist-administered CBT or a control condition emphasizing support and education (allocation 1:1:1). The acute treatment phase will last 10 weeks. Participants will undergo follow-up examinations two weeks after treatment ends (week 12) and three, six, nine, and 12 months after the end of treatment.

IBSOS requires the expeditious enrollment of a sufficient number of participants to ensure the statistical power and generalization of study results. This trial plans to recruit 480 participants over an approximately four-year treatment delivery period. Assuming a relatively conservative pre randomization dropout rate of 25%, each site will need to phone telephone screen approximately 150 participants per year and enroll (consent) 75 in order to meet yearly recruitment quotas of 60 randomized participants at each site.

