7.3 Preliminary Data Analysis

Prior to formal analysis, preliminary analyses will be conducted to provide perspectives on missing data, intent-to-treat analyses, attrition, normality of distributions, variance heterogeneity, non-model based outliers, *a priori* factor structures of multi-item instruments, reliability, and clustering (due to site).

For the primary questions, one set of analyses will establish whether the effects of MC-CBT and S-CBT are comparable. This will be pursued from two perspectives: a traditional hypothesis testing framework and an equivalence testing framework. For each outcome variable, there are assessments at baseline (BL), an immediate posttest (12W FU) and at three-, six-, nine-, and 12-month follow-ups (FU3, FU6, FU9 and FU12) for each of three groups (MC-CBT, S-CBT and an attention control, AC). The traditional analysis for a given outcome variable is a two-way analysis of covariance using the three groups as a between-participants factor, time as a within-participants factor (12W FU, FU3, FU6, FU9 and FU12) and the baseline score as a covariate. Single degree of freedom contrasts focus on the pairwise comparisons of adjusted means within a given time period (e.g. comparing MC-CBT, S-CBT and the AC). These analyses will reveal group differences on outcomes at different points in time. Because of the limitations of null hypothesis testing for asserting equivalence between two conditions, we will apply equivalence testing strategies to evaluate functional equivalence between conditions using methods described in Welleck ¹⁵. These methods will be applied in the context of the above analysis-of-covariance framework.

Another important analysis will be formal modeling of the long-term durability of acute treatment effects at three, six, nine, and 12 months post-treatment. Analyses will compare the decay functions of the different groups to determine if the decline (or improvement) in treatment effects from IM to FU12 differ depending on the type of treatment received. This will be pursued using SEM based growth curve modeling methods. The statistical technology for these analyses is described by Duncan et al ¹⁶.

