Another set of analyses will identify baseline participant characteristics that predict response to treatment and identify time varying mediators of response to treatment. For mediation analyses, both mediators and outcomes are measured at baseline as well as IM, FU3, FU6, FU9 and FU12. Most of the mediators also are measured during treatment, typically every other week as is an outcome proxy, the IBS symptom severity scale. One analytic strategy can be illustrated using IBS self-efficacy to predict within treatment variability in response to outcome at the immediate posttest (IM). An early response mediation model states that IBS self-efficacy gains experienced early in treatment (e.g. from B to W1 and W3) are the primary determinants of the ultimate response to treatment at IM. A recency mediation model states that the level of IBS selfefficacy at the last treatment session (W12) is the primary mediator of IM response to treatment. A growth curve mediation model states that it is the general acceleration/deceleration of IBS self-efficacy across the entire treatment session (as well as the shape of the curve) that best predicts response to treatment at IM (with IBS self-efficacy being as parameterized as a growth curve per Figure 1). A fourth model is one that incorporates all three types of mediational influence into a single estimating equation, with linear coefficients attached to each to reflect their relative influence in impacting treatment response. The baseline outcome variable is used as a covariate and the IM outcome is used as the criterion. All three sources of influences will be parameterized and modeled as predictors of change at IM as well as the decay functions characterizing change from IM to FU12. Models also will be pursued that include multiple mediators in the same model. Moderator analyses will be pursued by including product terms in the models.

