7.4. Formal Data Analysis

Aim 1

The primary focus of Aim 1 is to establish whether the effects of MC-CBT and S-CBT are comparable. We will pursue this from two perspectives: a traditional hypothesis testing framework and an equivalence testing framework. For the core outcome variables, we have assessments at baseline (BL), immediate post-test (FU W12) and at three-, six-, nine-, and 12-month follow-ups (FU3, FU6, FU9 and FU12) for each of three groups (MC-CBT, S-CBT and the active comparison control (attention control)). The traditional analysis for a given outcome variable is a two-way analysis of covariance

using the three groups as a between-participants factor, time as a within-participants factor (IM, FU3, FU6, FU9 and FU12) and the baseline score as a covariate. Single degree of freedom contrasts focus on the pair-wise comparisons of adjusted means within a given time period (e.g. comparing MC-CBT, S-CBT, and the attention control condition). Of interest is whether there are statistically significant pair-wise contrasts between the groups. We will pursue such contrasts using non-pooled error terms across time (because of the likely violation of sphericity), but with pooled error terms across groups within time (unless diagnostics suggest otherwise). We will use the program M Plus to estimate the single degree of freedom contrasts (by translating the analysis of covariance model into an SEM framework). M Plus has the capability to take into account cluster effects, should that be necessary, and it also offers robust algorithms.

In terms of statistical power, for a single degree of freedom contrast between two independent groups with a single covariate, the approximate sample size needed to achieve power of 0.80 for an adjusted mean difference of d = 0.50 (using Cohen's d) is approximately 65 per group. To achieve power of 0.90 requires a sample size of 85 per group. Our sample sizes easily meet these standards.

Aim 5

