Aims 2 and 3 emphasize identifying baseline participant characteristics that predict response to treatment (hence reflecting moderators of the effects of the interventions) and also identifying time-varying mediators of response to treatment. Response to treatment can be defined in terms of: (1) group differences in an outcome at a given point in time, (2) variation in decay functions after treatment, or (3) variations in change from baseline to the immediate post-test within a given group (i.e. within MC-CBT or within S-CBT). Statistical strategies vary depending on how response to treatment is operationalized.

With respect to mediation, an important facet of mediation analysis is specifying the correct time interval between the change in a mediator and change in the outcome of interest. Changes in a mediator may translate into instantaneous changes in an

outcome or, alternatively, it may take some time before the change in the mediator translates into change in the outcome. If one assesses the mediators after changes have occurred, but measures the outcome *before* the changes in the mediators have manifested themselves in the outcome, one is at risk of misdiagnosing the importance of the mediator. Unfortunately, the time dynamics by which mediator effects translate into outcome effects are not well understood in the IBS area. We will measure our mediators and outcomes at baseline as well as IM, FU3, FU6, FU9 and FU12. We also will measure most of the mediators during treatment, typically every other week, and we will gather a weekly assessment of an outcome proxy, the IBS symptom severity scale. This frequent assessment of mediators and outcomes has the advantage of allowing us to formally explore temporal dynamics with mediators and outcomes within the context of SEM frameworks.

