The richness of the data can be illustrated by considering one example; namely, IBS self efficacy used to predict within-treatment variability in response to outcome at the immediate post-test (IM), pooling the MC-CBT and S-CBT groups to bolster the stability of parameter estimates. IBS self efficacy is measured at baseline (BA) and during weeks 1, 3, 5, 7, 8 and 12 of the acute treatment phase (i.e. W1, W3, W5, W7, W8, W12). There are several plausible mediation models that may bear on results. An *early* response mediation model states that IBS self efficacy gains experienced early in treatment (e.g. from B to W1 and W3) are the primary determinants of the ultimate response to treatment at IM. A recency mediation model states that the level of IBS self efficacy at the last treatment session (W12) is the primary mediator of IM response to treatment. A growth curve mediation model states that it is the general acceleration/deceleration of IBS self efficacy across the acute treatment phase (as well as the shape of the curve) that best predicts response to treatment at IM (with IBS self efficacy being as parameterized as a growth curve per Figure 1). A fourth model is one that incorporates all three types of mediational influence into a single estimating equation, with linear coefficients attached to each to reflect their relative influence in impacting treatment response. The baseline outcome variable is used as a covariate and the IM outcome is used as the criterion. It is possible to use the M Plus software to parameterize all three sources of influences and then test their relative contributions. Note that this can be done to predict response to treatment as measured at IM or it can be used to predict decay functions characterizing change from IM to FU12. Models also can be pursued that include multiple mediators in the same model, thereby permitting complex multivariate explorations of the data.

Aim 4

The following section outlines the steps for the economic analysis of the costs and costeffectiveness of S-CBT and MC-CBT relative to the attention control group.

Aim 4A (Cost Hypothesis): The MC-CBT intervention will have lower costs per person than the S-CBT.

Aim 4B (Cost Hypothesis): Both S-CBT and MC-CBT will be cost-effective relative to the less costly but also less effective attention control. MC-CBT will be at least as effective as S-CBT, and given its lower costs, MC-CBT will be cost-effective relative to S-CBT.

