We will measure *global relief* of symptoms using two adequate relief measures. The original adequate relief measure was explicitly focused on adequacy of pain relief ^{43, 61} and does not necessarily estimate treatment response for IBS participants seeking relief from non-painful GI symptoms (e.g. diarrhea, urgency, bloating, etc). In our previous work ([name] et al., 2008), we therefore developed and validated a second adequate relief measure assessing adequacy of relief from bowel symptoms. Participants who respond affirmatively to the two adequate relief question(s) will be classified *a priori* as responders.

IBS Symptom Severity

We will adhere to the recommendation of Rome III to use the IBS-SSS ⁴⁹ to measure

IBS symptom severity. The **IBSSS** is a multidimensional patient-based rating scale of four domains (pain, distention, bowel dysfunction, and general well-being) deemed important to gauging overall IBS severity. Participants will complete the IBS-SS at baseline, and at each of the 5 follow-up assessments. Because the psychometric properties of the IBSSS are not firmly established⁶², participants will rate the overall severity of symptoms at the end of each week using a single-item global severity scale ("How severe have your IBS symptoms been in the last week?" with responses ranging from 0 = Absent; 1 = Mild, 2 = Moderate, 3 = Severe, 4 = Very severe).

The study GE will rate the global severity of IBS symptoms using the clinician version of the **CGI Severity of Illness Scale** ⁵⁹ (1 = normal, 7 = severely ill) at each of the main assessment periods.

Abdominal Pain / Discomfort

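### The recency mediator for Aim 3 is taken at the same week-12 visit as the outcome it should explain, and the in-treatment measurements the mediation plan describes do not match the schedule

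*Protocol*

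**What the plan says.** Section 7.4 (Aims 2 and 3) uses IBS self-efficacy to illustrate the mediation plan. It says the scale is completed at baseline and "during weeks 1, 3, 5, 7, 8 and 12 of the acute treatment phase". It then sets out four models for the outcome at the immediate post-test (IM):

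- early response: gains from baseline to weeks 1 and 3;
- recency: "the level of IBS self efficacy at the last treatment session (W12) is the primary mediator of IM response to treatment";
- growth curve: the course of self-efficacy over the acute phase;
- combined: all three influences in one equation, to compare their relative weight.

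Section 7.3 repeats the week-12 definition of recency. It says that all three influences will be modelled as predictors of change at IM and of the later decay functions.

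On timing, Section 2 states: "The acute treatment phase will last 10 weeks". Section 2.1 places week 12 two weeks after treatment ends. In Section 7.4, Aim 1, the first assessment after baseline is the "immediate post-test (FU W12").

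On the in-treatment outcome proxy, Section 7.4 says "we will gather a weekly assessment of an outcome proxy, the IBS symptom severity scale", while Section 7.3 says the mediators are measured "typically every other week as is an outcome proxy, the IBS symptom severity scale". Appendix 8 says: "Participants will complete the IBS-SS at baseline, and at each of the 5 follow-up assessments".

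**The concern.** Section 7.4 itself stresses that a mediation analysis depends on the right interval between change in the mediator and change in the outcome. When both come from one visit, the data cannot separate higher self-efficacy reducing symptoms from fewer symptoms raising self-efficacy. Time order carries particular weight in the worked example. It pools the two CBT arms to explain variation within treatment, so no randomised contrast supports a causal reading.

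The combined model adds a further difficulty. It sets a predictor measured at the outcome visit against predictors measured 9 to 11 weeks earlier. Two questionnaires completed at one visit share the participant's current state and reporting habits, so the concurrent predictor can be expected to look stronger whatever the true mechanism.

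The promise to explore temporal dynamics during treatment also rests on frequent measurement of both mediator and outcome. If the scheduled forms do not deliver that frequency, the analysis cannot be done on the named scale.

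**Working it through.** No sample-size or power figure bears on this point. The check sets the stated measurement weeks against the schedule.

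**Step 1: identify IM.** Section 7.3 gives the within-participant time factor as 12W FU, FU3, FU6, FU9, FU12. Section 7.4 gives the same factor as IM, FU3, FU6, FU9, FU12. IM is therefore the week-12 follow-up.

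**Step 2: locate week 12 relative to treatment.** Treatment ends at week 10, and 12 − 10 = 2 weeks after the end. Week 12 is neither a treatment session nor part of the acute phase.

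**Step 3: lag between mediator and IM outcome.** Appendix 7, Book 3, marks the self-efficacy questionnaire, the symptom severity scale and the Global Impression of Change in the same week-12 column.

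- Recency as written: 12 − 12 = 0 weeks. The global improvement item asks about the past week (Appendix 8), so the period it rates comes before or overlaps the mediator score.
- Early response: 12 − 1 = 11 and 12 − 3 = 9 weeks. Time order holds.
- Last scheduled point before IM (week 8): 12 − 8 = 4 weeks. Appendix 8 lets the post-treatment visit fall in weeks 10 to 14, so the range is 10 − 8 = 2 to 14 − 8 = 6 weeks. Process measures may be completed up to seven days after they are assigned, which can take one more week off.
- Week-12 mediators against the 3-month follow-up, shown as week 22 in Book 3: 22 − 12 = 10 weeks. Time order holds.

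**Step 4: self-efficacy points in the acute phase.** Section 7.4 lists six: weeks 1, 3, 5, 7, 8 and 12. Book 2 marks weeks 1, 3, 5 and 8, plus premature discontinuation. Week 7 has no entry and week 12 belongs to follow-up: 6 − 2 = 4. The locus-of-control, perceived-stress and two-item coping rows show the same pattern.

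**Step 5: symptom severity scale during the 10 treatment weeks.**

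| Source | Stated frequency | In-treatment points |
|---|---|---|
| Section 7.4 | weekly | 10 |
| Section 7.3 | every other week | 10 / 2 = 5 |
| Appendix 8 | baseline and five follow-ups | 0 |
| Appendix 7, Book 2 | week 5, plus premature discontinuation | 1 |

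The four sources give four different counts. One in-treatment point, even with baseline and week 12, cannot support a lead-lag analysis within treatment.

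**Step 6: what is collected weekly.** Appendix 8 has participants rate overall symptom severity on a single five-category item at the end of each week of acute treatment. It also has daily pain, bloating and urgency ratings.

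**The case against.** Several points against the concern have force.

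- The self-efficacy models are offered as one example for a secondary aim, and a final mediator specification normally belongs in the SAP. This stands in part. But Section 7.3 says the three influences will be modelled, and the protocol has already fixed week 12 and mislabelled it. That is an internal contradiction, not a detail left for later.
- Section 7.4 allows that a mediator may act on the outcome at once, so a concurrent component is defensible. This stands, provided that the component is labelled as an association.
- The weekly proxy may loosely mean the weekly single item. That is possible, but the name used is that of the symptom severity scale, which has its own form in the schedule. The naming still needs correcting.
- The schedule tables were read from a damaged source. The Book 2 rows used here keep their columns and agree with one another. The week-12 error and the conflict among Sections 7.3, 7.4 and Appendix 8 do not depend on them.

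A reader might infer that Aim 3 as a whole cannot establish time order. The documents do not support that. The early-response model, a growth curve ending at week 8, and week-12 mediators predicting the 3- to 12-month outcomes all keep the mediator first. Nor are the in-treatment mediator measurements absent: four points are scheduled, which roughly fits the statement that most mediators are measured about every other week. Data on the symptom severity scale during treatment are sparse, not missing.

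**Conclusion.** The point holds in a limited form. At IM, the recency model, the combined model, and any mediator growth curve that includes week 12 relate measurements from one visit (lag 0 weeks) and cannot show time order. The expected tilt towards recency follows from shared-occasion measurement. It is a direction only, and the documents give no figure from which to size it.

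The schedule delivers four acute-phase self-efficacy points against six stated, and one in-treatment point on the symptom severity scale against 10 or about 5. The within-treatment lead-lag analysis on that scale is therefore unsupported.

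These counts assume that the Book 2 columns are read correctly. Only secondary Aim 3 analyses are affected; no primary or safety conclusion changes. The point should be corrected before the mediation models are fitted.

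**What to change.** 1. For models of the IM outcome, define recency as self-efficacy at week 8, the last scheduled point before IM, and state the lag (nominal 4 weeks, about 2 to 6 with the visit window).
2. Fit the mediator growth curve for IM to baseline and weeks 1, 3, 5 and 8 only.
3. Keep any model of IM that uses week-12 mediators only if it is labelled a concurrent association. Use week-12 mediators as lagged predictors of the 3-, 6-, 9- and 12-month outcomes.
4. Name the weekly single-item global severity rating as the in-treatment outcome proxy.
5. Reconcile Sections 7.3 and 7.4, Appendix 7 and Appendix 8 on week 7, on week 12, and on the frequency of the symptom severity scale.

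This is a change of wording, and no new data are needed. There are two real costs. Week 8 misses the last two weeks of treatment, including the final MC-CBT clinic visit as Book 2 appears to place it, so the revised model tests a somewhat different hypothesis from self-efficacy at the end of therapy. The single item is also coarser than the symptom severity scale.

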Aim 5 emphasizes evaluating the long-term durability of acute treatment effects at three, six, nine, and 12 months post-treatment. Accordingly, a second type of analysis will compare the decay functions of the different groups, to determine if the decline (or improvement) in treatment effects from IM to FU12 differ depending on the type of treatment received. For example, it might be found that the beneficial effects of MC-CBT decline more rapidly than S-CBT in the months following the completion of the formal treatment regimen. This can be tested using growth curve analysis in an SEM framework. For a single outcome and a linear growth curve, the basic growth curve model is parameterized using figure 1. The three treatment groups are represented by two dummy variables. The intercept represents the score at IM and the slope represents the linear decay function. The path coefficients from the dummy variables to the latent slope variable represents group differences in the average slope characterizing the decay function. The statistical technology for executing these analyses is straightforward and well-developed ^{16, 17}. It is possible that the decay functions are nonlinear. One strategy for modeling non-linear trajectories is to use guadratic regression, but this can yield parameter estimates that are difficult to interpret or the non-linearity may not be quadratic in form. An alternative approach is to use spline regression in which meaningful spline knots are identified and then slopes are measured between knots. This approach is readily incorporated into growth curve analyses and involves representing each slope defined by knots as a distinct latent variable. We will use M Plus to estimate the parameters of the growth curve. The program has the capability to take into account cluster effects due to site, should that be necessary, and it also offers robust algorithms.

In terms of statistical power, using the power analysis methods described by Raudenbush ¹⁸, we set the duration parameter at 4, the frequency of observations at 1, the standardized effect size reflecting the ratio of the group mean difference to the standard deviation of the true change component at 0.50, the within-person variance at

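### The combined mediation model's coefficients cannot be read as relative influence, because early gain, week-12 level and growth curve are overlapping functions of one self-efficacy series

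*Protocol*

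**What the plan says.** Protocol section 7.4, under Aims 2 and 3, takes self-efficacy as its example: "IBS self efficacy is measured at baseline (BA) and during weeks 1, 3, 5, 7, 8 and 12 of the acute treatment phase". It sets out three mediation models for the outcome at the immediate post-test, with the two CBT arms pooled:

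- early response: "self efficacy gains experienced early in treatment (e.g. from B to W1 and W3";
- recency: "the level of IBS self efficacy at the last treatment session (W12";
- growth curve: the general course and shape of change, "with IBS self efficacy being as parameterized as a growth curve per Figure 1".

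A fourth model "incorporates all three types of mediational influence into a single estimating equation, with linear coefficients attached to each to reflect their relative influence". Mplus is then named as able to "parameterize all three sources of influences and then test their relative contributions". Section 7.3 states it as a commitment: "All three sources of influences will be parameterized and modeled as predictors of change at IM", and extends it to the post-treatment decay functions.

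Neither section mentions that the three predictors come from one series of scores, or says whether early gain and week-12 level enter as observed or latent quantities. The growth curve follows Figure 1, whose slope the Aim 5 text describes as latent.

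**The concern.** A regression coefficient measures what a predictor adds with the others held fixed. Early gain and final level are parts of the growth trajectory, so holding the trajectory fixed removes most or all of what they represent. A coefficient on what is left does not say how much early change or final level matters.

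The stake is an Aim 3 statement about how CBT works. Read as the protocol describes, the table of coefficients could give a true mechanism a small weight, or a false one a large weight of either sign, depending on which curve the analyst fitted.

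**Working it through.** The protocol gives no sample size, power or error figure for the mediation models, so there is no stated number to reproduce. The check is algebra plus fits to assumed population covariances.

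**1. Both terms read as points on the fitted curve.** With intercept i and weekly slope s, the linear curve gives:

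- early gain (baseline to week 3) = 3s;
- week-12 level = i + 12s.

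With a quadratic term q, these become 3s + 9q and i + 12s + 144q. In both cases they are exact linear combinations of the growth factors. The combined equation has two more predictors than independent dimensions, so its coefficients are not identified.

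**2. Both terms read as observed scores.** Early gain is now 3s plus the difference of two occasion errors, and week-12 level is i + 12s plus one. Given i and s, only occasion error and any departure from the fitted curve remain.

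Inputs:

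- Reliability of one score, 0.83: internal consistency of the self-efficacy scale in Appendix 8, used here as an assumption about occasion error.
- Assumed, not in the documents: true baseline SD 1; independent true early gain (to week 3) and late gain (week 3 to 12), SD 0.5 each; a true standardised effect of 0.50.
- Occasions: baseline and weeks 1, 3, 5, 8 and 12.

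Error variance = (1 - 0.83)/0.83 = 0.205. Reliability of the observed gain = 0.25/(0.25 + 2 x 0.205) = 0.38. With gain SD 1 it is 1/(1 + 0.41) = 0.71.

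Maximum-likelihood fit of the combined model to the population covariance, equal error variances, standardised coefficients:

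| Truth | Fitted curve | Early gain | Last level | Growth factors |
|---|---|---|---|---|
| Early gain only, 0.50 | linear | 0.17 | -0.44 | slope 0.52 |
| Early gain only, 0.50 | quadratic | 0.08 | +0.52 | share the rest |
| Final level only, 0.50 | linear | about 0 | 0.03 | intercept 0.38, slope 0.25 |

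In the first two rows the true coefficient of last level is zero. The model gives it a large weight whose sign depends on whether the curve is linear or quadratic. A second set of assumed variances, using all seven occasions in the text, shows the same reversal: last level -0.37 (linear) and +0.60 (quadratic).

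The third row depends on the settings. With gain SD 1, last level is 0.09 to 0.10 if error variances are held equal across occasions and 0.24 if they are free.

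**3. Other trajectory shapes (reliability 0.83, true effect 0.50).**

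| Scenario | Truth | Early | Last | Growth (joint) |
|---|---|---|---|---|
| Linear growth, pure measurement error | any of the three | 0.00 | 0.00 | 0.50 |
| Real occasion-specific deviations | early | 0.33 | 0.00 | 0.09 |
| Real occasion-specific deviations | final level | 0.00 | 0.24 | 0.26 |
| Autocorrelated deviations, linear fit | early | 0.29 | -0.08 | 0.17 |
| Autocorrelated deviations, linear fit | final level | about 0 | 0.32 | 0.19 |
| Autocorrelated deviations, quadratic fit | early | 0.22 | 0.40 | 0.52 |
| The observed score itself drives the outcome | early or final level | 0.50 for the true term | 0.50 for the true term | 0.00 |

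Only the last scenario returns the true single-score term at full size, and it requires measurement error itself to affect the outcome.

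**4. Non-overlapping components.** In the step 2 population under early-gain truth, a latent model with baseline level, early slope and late slope returns 0.50 for the early slope and 0.00 for the rest. Under final-level truth it returns equal unstandardised weights on the three parts, as it should, since final level is their sum.

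**The case against.** Several points on the other side stand.

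- **Observed-score entry is an inference.** The protocol leaves the parameterisation open, and such detail may sit in an analysis plan not shown. This does not rescue the stated reading: the curve-based version is not identified, and the observed-score version does not measure relative influence.
- **A reader might infer that the model favours the growth curve whichever mechanism is true.** The documents do not support this. With real occasion-specific deviations, early truth gives early 0.33 against growth 0.09. With autocorrelated deviations and a linear curve, the true single-score term again exceeds growth. The direction depends on features the protocol does not fix.
- **A reader might infer that loading on the slope under linear growth is bias.** It is not. If growth is strictly linear, early gain is 3 x the weekly slope, so the two are one hypothesis and no analysis can separate them.
- **The illustration fits the wrong curve to a bent trajectory.** This is partly fair. With free error variances the linear fit has a discrepancy of 0.115, a noncentrality of about 320 x 0.115 = 37 on 14 degrees of freedom at 160 per CBT arm, so a fit test would very probably reject it. But the natural next step, a quadratic, turns the false last-level coefficient from negative to positive.
- **The setting is secondary and largely exploratory.** Section 7.4 introduces the models through one example. The Aim 3 hypotheses ask whether control beliefs and nonspecific factors mediate change, not whether early, final or overall change matters most. The three separate models remain. A reader who concludes that Aim 3 as a whole fails would go too far.

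**Conclusion.** The point holds in limited form. The protocol says the joint coefficients of the fourth model reflect relative influence, and under neither available definition of the terms do they. The identification result is algebra and needs no assumed numbers.

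The illustrative sizes (early about 0.17, slope about 0.52, last level about -0.44 or +0.52 when only early gain acts, with effect 0.50) rest on assumed separate early and late gains of SD 0.5, reliability 0.83, independent occasion errors and a bend at week 3. Other assumptions change the size and the direction, so no general claim of bias towards one mechanism is justified. The consequence is confined to how a secondary mechanism analysis is interpreted; the primary endpoint and the sample size are untouched.

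**What to change.** Remove the statement that the joint coefficients show relative influence, in sections 7.3 and 7.4. Replace the fourth model with one built on non-overlapping latent components: baseline level, early slope and late slope. The Aim 5 text already names the tool: "spline regression in which meaningful spline knots are identified and then slopes are measured between knots", with each slope a distinct latent variable.

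Regress the outcome on the three components, coded as baseline level and total change in each segment, with coefficients b0, b1 and b2. Each theory is then a restriction:

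- early response: b0 = b2 = 0;
- final level: b0 = b1 = b2;
- overall growth, taken as total gain: b0 = 0 and b1 = b2.

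Test each against the unrestricted model by likelihood ratio, and compare the theories with one another by BIC. Comparing them as separate models by BIC would also do.

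Pre-specify the knot and vary it in a sensitivity analysis. Week 3 follows from the protocol's own early-response example, but it is also the bend assumed in the check above, so its good performance there is not independent evidence for it. State that early gain and overall slope cannot be told apart if growth is linear.

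The cost is revised wording, slightly more complex Mplus code, and wider intervals for the early slope, which rests on three occasions (baseline, weeks 1 and 3). No new data are needed.
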